4. SUBJECT AND SITE SELECTION

4.1. Accrual

As part of current care, patients are identified by a provider in the ED as needing psychiatric evaluation, and a referral is made to the telepsychiatric provider for a virtual consult. Patients are eligible to be included in analysis for the project if they meet the inclusion criteria and the telepsychiatric consultation occurs during potential BH-VPN program hours. We will accrue patient data for evaluation during a period starting in October 2019. Based on prior data, we estimate about 1,100 patients will complete a telepsychiatric consult in a 14-month period. Patients will not be accrued on days/times when the navigators would be not available (e.g. holidays).

Once a patient is in the intervention arm, the patient remains in the intervention arm until 45 days, or if there is a failure to contact (4 phone calls in 12 days), if the patient becomes enrolled with a case management program, declines services, or if the patient dies.

4.2. Eligibility Criteria

4.2.1. Inclusion Criteria

Eligible patients must meet each of the following criteria:

- Present to an ED at participating sites
- Complete a telepsychiatric consult as captured in the electronic medical record
- Complete a telepsychiatric consult during the navigator's hours of operation (Monday-Friday 7AM to 11PM and Saturday 7AM to 7PM)
- ≥ 18 years of age at time of ED admission

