5.3. Behavioral Health Virtual Patient Navigation (BH-VPN) Program

The BH-VPN outlines the flow of patients from initial contact to their follow-up calls (see Appendix 1). In the existing ED workflow, patients are identified by a clinician in the ED as needing psychiatric evaluation and a referral is made to a tele-psych provider for a virtual consult. Patients who complete a telepsychiatric consult in the ED can be enrolled to either the control or intervention arm based on a randomization scheme that randomly allocates days that navigators are available. Psychiatrists are reminded through daily communication as to whether the BH-VPN program is available and the ED locations. The psychiatrist will make a recommendation to admit or discharge the patient. The ED physician will make the final decision on whether to admit or discharge the patient from the ED. Patients that have a discharge recommendation on days the program is available, will be offered the BH-VPN program. Enrolled patients are followed for up to 45 days.

If a discharge recommendation is made, a patient will be approached again by the navigator virtually for enrollment into the BH-VPN program. The patient has the option not to be followed by the navigator. Before discharge, the navigator will complete an initial virtual behavioral health assessment. The initial health assessment contains information such as preferred communication method, primary care provider, psychiatry provider, PHQ-9 screening, collateral resources, recent ED and hospital utilization, substance use disorder, medication barriers, appointment barriers, community resources, and crisis planning.

The follow-up assessments, which will occur during navigation phone calls at least weekly, may include information such as a suicide ideation safety screening, an appointment reminder, appointment barrier evaluations, medication obtainment follow-up, substance use disorder follow-up, PHQ-9 screening, supportive listening, psychoeducation, community resource follow-up, and additional crisis planning. Phone calls are weekly as standard care but may be more often depending on the individual needs of the patient. Appointments are dependent on a patient's specific needs and may be with a therapist or psychiatrist as well as other providers in the community such as primary care or referral to a community provider.

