6. DATA COLLECTION AND REPORTING

Patient demographics, comorbid conditions, and utilization will be obtained from the electronic medical record and billing systems. Data from the initial assessment and follow-up contacts will be stored in HealtheCare, a care management platform in Cerner. Data will be retrieved by an application specialist on the research team. Data may be retrieved retrospective to a patient's completion of the intervention or usual care arm of the study.

A bi-monthly report will be produced for the intervention arm. The report will be by ED site and overall.

- Count of patients meeting the inclusion criteria
- Count of patients with a HealtheCare account
- Count of patients enrolled in the BH-VPN program
- Patient list with their enrollment status in HealtheCare

A monthly report will be produced for the intervention arm. The report will be by ED site and overall. Report to be generated following the end of the previous month.

- Count of patients meeting the inclusion criteria
- Count of patients with a HealtheCare account
- Count of patients enrolled in the BH-VPN program

- Patient list with their enrollment status in HealtheCare

An Annual report will be prepared for the Duke Foundation measures.

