6.1. Sample size analysis and statistical analysis

Given the preliminary data from our previous study, we will power the proposed study to detect at least an 8% absolute difference between hospital admission in the VIBRANT intervention and usual care groups. The usual care group is assumed to have a 60% inpatient admission rate based on prior data. There is 85% power to detect this reduction with a total sample size of 1,030 ($\alpha=0.05$) using a Chi-square test for independence. To account for the possible correlation among patients seen in the ED on the same day, we inflated the sample size by 10% assuming the average number of patients per ED per day is 2 with a 0.1 intra-class correlation coefficient (design effect = $1 + (2-1)*ICC$).¹⁴ Thus, the target sample size is $n=1,133$. The power was calculated using PASS 15 Power Analysis and Sample Size Software (2017). NCSS, LLC. Kaysville, Utah, USA, ncss.com/software/pass.

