8.1. Protocol and Pathway Training

Background, protocol and process steps will be presented to psychiatrists and nurse practitioners who will be providing virtual psychiatric consultations. The role of virtual patient navigator and randomization scheme will be presented so expectations are clear that this is not available every day/time or weekends. This will be presented at the Department of Psychiatry meeting, which includes Emergency and Telepsychiatry Departments. Attendees may also include providers, who at some point may see patients who have been through this pathway but will not be directly involved in providing evaluations. Education will be provided to the emergency department staff involved in this project, so that they are aware of the process and the role of the virtual patient navigator.

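### Patients enter the analysis through an ED referral and completed consult after the day's arm is fixed, and no between-arm comparison of consult volume or of admissions per randomized ED-day is prespecified

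*Combined protocol and SAP*

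**What the plan says.** Section 5.2 labels each day as program or usual care for the whole study, with three days of each per week, and a patient's arm follows the day and time of the first consult. Entry comes afterwards. Under Section 5.3, "patients are identified by a clinician in the ED as needing psychiatric evaluation and a referral is made to a tele-psych provider", and Section 4.2.1 requires that the patient "Complete a telepsychiatric consult as captured in the electronic medical record". Section 4.3 takes everyone who meets those criteria as the intention-to-treat set, and Section 6.2 compares the proportion admitted between arms within that set.

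The setting is open. Section 5.3 has psychiatrists reminded daily whether the program is running. In Section 8.1, "Education will be provided to the emergency department staff involved in this project", covering the process and the navigator's role.

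On monitoring, Section 6 states that "A monthly report will be produced for the intervention arm", and a bi-monthly report has the same scope. Both include the number of patients meeting the inclusion criteria. An annual report covers the foundation measures. The synopsis words the first of these as a count of consulted patients in both arms; Sections 1.4 and 5.1.3 give the same measure without naming arms. Section 5.1.2 lists the baseline variables as age, race, gender and Charlson score.

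**The concern.** The primary outcome is a proportion whose denominator is formed after allocation by staff who may know the arm. A completed consult on a program day is the route to a navigator. It is therefore plausible that a borderline patient, likely to go home anyway, is referred or has the consult completed more readily on such a day. Extra low-risk patients would lower the program-arm admission rate without any change in anyone's care, and in the direction of the hypothesis.

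The intention-to-treat analysis does not protect against this, because it conditions on having been consulted. Covariate adjustment under Section 6.2 would not repair it either: none of the listed baseline variables measures psychiatric severity. The plan names no comparison that would bring a difference in consult volume to the reader's attention.

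**Working it through.** **Inputs from Section 6.1.** "The usual care group is assumed to have a 60% inpatient admission rate based on prior data"; the study is powered to "detect at least an 8% absolute difference between hospital admission", that is 60% against 52%; the design effect is 1 + (2 − 1) × 0.1 = 1.1; the target is 1,133. Section 6.2 makes tests two-sided, and Section 5.2 gives equal numbers of days per arm.

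**The plan's own figure.** The inflation reproduces: 1,030 × 1.1 = 1,133. The 1,030 does not. At two-sided 0.05 and 85% power, n per arm = [1.96√(2 × 0.56 × 0.44) + 1.036√(0.60 × 0.40 + 0.52 × 0.48)]² / 0.08² = (1.3759 + 0.7252)² / 0.0064 = 689.8, so 690 per arm and 1,380 in total; power at 1,030 is about 73.5%. That is a separate matter. Here 1,133 serves only as the planned size.

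**Assumed inputs (not in the documents).** No true effect; program days bring a fraction e of extra consults, admitted at rate r.

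1. Program-arm rate = (0.60 + e × r) / (1 + e). For e = 10%, r = 20%: 0.62 / 1.10 = 56.4%, a false reduction of 3.6 points.

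2. Chance of a significant false benefit, from a pooled two-proportion z-test with variance × 1.1 (an approximation to the planned mixed model). The 1,133 patients split 1 : 1.1 into 539.5 and 593.5. The pooled rate is 0.581, and the null standard error is √[1.1 × 0.581 × 0.419 × (1/539.5 + 1/593.5)] = 3.08 points. Significance needs 1.96 × 3.08 = 6.03 points. The probability is Φ[(3.64 − 6.03) / 3.07] = Φ(−0.78) = 21.8%. A simulation with Poisson consult numbers gives about 21%; it draws patients independently while the test keeps the 1.1 factor.

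| e | r | Program-arm rate | False reduction (points) | P(significant false benefit) |
|---|---|---|---|---|
| 5% | 10% | 57.6% | 2.4 | 11.8% |
| 5% | 20% | 58.1% | 1.9 | 9.0% |
| 5% | 30% | 58.6% | 1.4 | 6.8% |
| 10% | 10% | 55.5% | 4.5 | 31.3% |
| 10% | 20% | 56.4% | 3.6 | 21.8% |
| 10% | 30% | 57.3% | 2.7 | 14.2% |
| 20% | 20% | 53.3% | 6.7 | 57.5% |
| 25% | 20% | 52.0% | 8.0 | 72.9% |

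The nominal figure in the favorable direction is 2.5%. With r = 20%, imitating the full 8 points takes a share of 0.08 / (0.60 − 0.20) = 20% of the program arm, that is 0.20 / 0.80 = 25% more consults.

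3. Admissions per day move differently in expectation. With e = 10% and r = 20% they change by 0.62 / 0.60 = +3.3%; a true drop to 52% changes them by 0.52 / 0.60 = −13.3%.

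4. Sensitivity of a plain count comparison, z = (n₁ − n₀) / √(n₁ + n₀). A 10% excess gives (593.5 − 539.5) / √1,133 = 1.60, so power is Φ(1.60 − 1.96) = 36%. A 20% excess gives (618 − 515) / √1,133 = 3.06, so power is 86%. Counts are taken as Poisson; extra day-to-day variation would lower both.

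5. Value of a direction rule, by the same simulation. If a benefit also had to show fewer admissions in the program arm, false claims would fall from about 21% to 15% (10% extra, 20% admitted) and from about 58% to 19% (20% extra, 20% admitted). Power under a true 8-point effect stays near 74%.

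**The case against.** A reader might infer that eligible patients are counted in the intervention arm alone, so that a difference in denominators could never be seen. The documents do not support that. The synopsis lists consult counts for both arms, the foundation measures are reported yearly, Section 9.2 has the team, including the statistician, review enrollment as needed, and both arms' totals will be known at analysis. The intervention-arm reports also look operational, since they track navigator enrollment. A large excess would be visible. What stands is that nothing says the totals will be compared or how a difference would be read.

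A reader might also infer that ED clinicians know each day's arm and will refer accordingly. Section 5.3 sends the daily message to psychiatrists, and no passage sends it to referring clinicians. Section 8.1 describes education, not a daily notice. Section 4.1 presents referral as part of current care, and the navigator's contact is virtual. Differential referral is therefore a possibility, not a finding, and every value of e and r above is assumed. Against that, psychiatrists, who complete the consult that defines entry, do know the arm, and ED staff know how the program works.

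Finally, one might infer that a per-day admission count cleanly separates a true effect from a referral artifact. That holds for expected values only. In the 10% case most false claims survive the direction rule (15 of 21 percentage points), so it should not become a formal gate on the primary claim.

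**Conclusion.** The point holds as a gap in safeguards. Entry follows allocation in an unblinded setting, the primary analysis conditions on entry, the listed covariates do not capture psychiatric severity, and no comparison of consult volume or of admissions per randomized ED-day is prespecified. The documents do not show that referral or completion will differ between arms.

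If it did, modest shifts would matter. At 30% to 10% admission among the extra patients, 5% more consults give a false reduction of 1.4 to 2.4 points, and 10% more give 2.7 to 4.5 points, with a 14% to 31% chance of a significant false benefit. These figures assume no true effect, a 60% base rate, 1,133 patients and the plan's design effect of 1.1.

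**What to change.** 1. In Section 6, report the number of patients meeting the inclusion criteria for both arms, by ED. Reconcile the wording of the consult-count measure across the synopsis, Section 1.4 and Section 5.1.3.

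2. In Section 6.2, prespecify a supporting analysis over all randomized eligible ED-days, including days with no consults. Compare by arm (a) consults per ED-day and (b) admissions among consulted patients per ED-day. Use a count model with the log of eligible hours as offset, since Saturday has 12 hours and weekdays 16. Report both with confidence intervals beside the primary odds ratio. Referral cannot alter the denominator of ED-days.

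3. State that the primary result will be interpreted with caution if consult volume differs by arm or if the per-day admission result disagrees with the proportion. Do not make the primary claim formally conditional on the direction of the per-day count.

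The cost is small: an existing report is extended to the usual-care arm, and one supporting analysis is added on data already being retrieved. The check is less precise than the primary analysis and is weak for small shifts. Its numerator still covers only consulted patients, so it would not by itself reveal likely admissions that went without a consult on program days. It is a partial safeguard.

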4.2.2. Exclusion Criteria

- Patients currently enrolled in the BH-VPN program upon their index ED encounter

4.3. Evaluable Population

Patients included in the evaluable population for this project, will contribute data to the final outcomes assessment. All patients who meet the inclusion criteria will be assessed for the primary outcome (intent to treat). Patients will have one of the following ED discharge dispositions: (admission to the hospital for medical reasons, admission to a behavioral health facility by voluntary or involuntary commitment, discharge from the ED, or death). A patient will contribute to the analysis once, using their initial enrollment to either arm of the study.

5. OVERALL DESIGN

5.1. Outcome Variables

5.1.1. Primary Outcome Variable

The primary outcome variable is ED to hospital admission. This is a patient that presents to an Atrium Health ED and then is admitted for any reason. A patient's disposition is tracked in the electronic medical record. The disposition is simply indicated as admitted or not admitted.

5.1.2. Rates and Variable Descriptions

- a. Demographic characteristics (age, race, gender)
- b. Charlson comorbidity index score

- c. Patient-centric defined 45-day utilization rate. This is a utilization rate among patients with an ED, inpatient, or observation encounter to any Atrium Health facility (≤ 45 days after the ED admit date)
- d. Frequency of self-harm diagnoses within 45 days of the index ED encounter at any Atrium Health location facility (≤ 45 days after the ED admit date)
- e. Frequency of patients who return to the ED and have a telepsychiatric consult (≤ 45 days after the ED admit date)

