Study Objectives	
Primary objective:
 
 • Compare the effectiveness of having the Behavioral Health – Virtual Patient Navigation (BH-VPN) program available compared to usual care, on admission rates among patients in the ED with a telepsychiatric consult 
Secondary objectives:
 
 • Compare demographics and Charlson comorbidity score between the two arms of the study • Compare the patient-centric 45-day utilization rate after the ED visit (ED, IP, OBS, encounter) between the 2 arms of the study • Compare the frequency of patients with an encounter with a self-harm diagnosis within 45 days of the ED visit between the 2 arms of the study • Compare the frequency of patients who return to the ED and have a telepsychiatric consult within 45 days of their initial ED visit between the 2 arms of the study 
Reporting for the Duke Foundation:
 
 • Count/frequency of patients in the intervention and usual care arms presenting to an ED that have a telepsychiatric consult during the intervention • Count/frequency of patients with an admission after telepsychiatric consult in the intervention arm • Count/frequency of patients active in the BH-VPN • Count/frequency of patients active in the BH-VPN program that had an encounter with a self-harm code within 45 days of their ED visit • Count/frequency of patients active in the BH-VPN program that have an acute care visit (ED, IP, OBS) within 45 days of their ED visit • Count/frequency of patients active in the BH-VPN program that return to an Atrium Health emergency department with a telepsychiatric consult within 45 days of their ED visit • Count/frequency of patients active in the BH-VPN program that improve their PHQ-9 score, among patients with an initial score >10

	
 • Count/frequency of active in the BH-VPN program that report suicide ideation on their initial PHQ-9 (Q2>0), that no longer report suicide ideation on their last PHQ-9 (Q2=0) • Count/frequency of patients active in the BH-VPN program with successful case closure (complete the program or have a successful referral in care)

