
Inclusion/ Exclusion Criteria
	
Inclusion:
 
 • Present to an ED at participating sites • Complete a telepsychiatric consult as captured in the electronic medical record • Complete a telepsychiatric consult during the navigator’s hours of operation • ≥ 18 years of age at time of ED encounter 
Exclusion:
 
 • No exclusions

Study Procedures
	
Patients are identified by a clinician in the ED as needing psychiatric evaluation and a referral is made to a tele-psych provider for a virtual consult. Patients who complete a telepsychiatric consult in the ED can be enrolled to either the control or intervention arm based on a randomization scheme that randomly allocates days that navigators are available. Psychiatrists are reminded through daily communication as to whether the BH-VPN program is available and the ED locations. The psychiatrist will make a recommendation to admit or discharge the patient. For patients that have a discharge recommendation on days that BH-VPN is available, patients will be offered the BH-VPN program. Enrolled patients are followed for up to 45 days. Each patient will receive the following core components:
 
 1. Introduction to the patient follow-up process prior to discharge 2. Follow-up evaluation within 72 hours by phone and weekly contact 3. Confirm that an in-person follow-up visit with an appropriate provider or clinician is scheduled. Where applicable, confirm in-network follow-up appointments are completed. 4. Ongoing assessment: substance use disorder, medication barriers, and appointment barriers 5. Assist with community resources, crisis planning, and supportive listening 6. Placement into an appropriate case management program, if needed. 
On days where the navigator is available, all patients who meet eligibility criteria will be considered exposed to the intervention; whereas, on days the navigator is not available all patients will be considered exposed to usual care.

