1.3. Secondary Objectives

The secondary objectives are to compare the behavioral health – virtual patient navigation team’s effect on additional patient outcomes

- I. Compare the patient-centric 45-day utilization rate after the ED visit (ED, IP, OBS, encounter)
- II. Compare the frequency of patients with an encounter with a self-harm diagnosis within 45 days of the ED visit
- III. Compare the frequency of patients who return to the ED and have a telepsychiatric consult within 45 days of their initial ED visit

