3. RATIONALE

To enhance the care of patients with a telepsychiatric consult, Atrium Health has designed a Behavioral Health Virtual Patient Navigation (BH-VPN) program. Navigators will monitor patients and assist with navigation through a weekly phone call after their index ED encounter for up to 45 days post ED discharge. The BH-VPN aims to improve patient outcomes through standardized approaches that leverage analytics and technology, while bridging care coordination. When a patient presents to a participating Atrium Health ED, those with a telepsychiatric consult completed on a randomized intervention day, during the hours of operation, are provided the option of participating in the BH-VPN program. A patient can choose not to receive care by a navigator post discharge.

The BH-VPN program includes the following key components: introduction to the patient follow-up process prior to ED discharge, follow-up evaluation within 72 hours by phone and weekly contact, confirmation that a follow-up visit is scheduled, where applicable confirm in-network follow-up appointments are completed with an Atrium Health provider, and placement into an appropriate case management program, if needed. There may be cases where patients are eligible to enroll in full case management programs based on their insurance and other criteria. For example, if a patient has Medicaid through Cardinal Innovations, a managed care organization providing local behavioral health care, and meets specific criteria, would no longer require navigation services. A patient's contact with the BH-VPN program ends after 45 days following ED discharge, or if there is a failure to contact, becomes enrolled with a case-management program, declines services, or the patient dies. For those patients enrolled in a case management program, then navigator will ensure the patient is in contact with case management program staff before ending contact with the patient.

This research project is a pragmatic, randomized evaluation of a quality improvement initiative which seeks to evaluate the effects of standardizing the use of a BH-VPN program among patients with a telepsychiatric consult. The outcomes evaluation of this intervention has been designed to integrate with routine care and minimize frontline staff burden by deploying an evaluation in a real-world setting.

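### The 45-day self-harm comparison accepts codes from any Atrium encounter, including outpatient visits that BH-VPN helps patients attend, so it is exposed to unequal detection of unknown size and direction

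*Combined protocol and SAP*

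**What the plan says.** **The outcome.** Section 1.3 sets the objective: "Compare the frequency of patients with an encounter with a self-harm diagnosis within 45 days of the ED visit". Section 5.1.2(d) defines the variable as "Frequency of self-harm diagnoses within 45 days of the index ED encounter at any Atrium Health location facility", with the window running to 45 days after the ED admit date. No encounter type is named. Item (c) in the same list does name them: "This is a utilization rate among patients with an ED, inpatient, or observation encounter to any Atrium Health facility". The foundation reporting lists in Sections 1.4 and 5.1.3 likewise keep encounters with a self-harm code separate from acute care visits.

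**The data source.** Section 6 states: "Patient demographics, comorbid conditions, and utilization will be obtained from the electronic medical record and billing systems". No source outside Atrium is named.

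**The intervention.** The synopsis (Study Procedures) includes as a core component: "Confirm that an in-person follow-up visit with an appropriate provider or clinician is scheduled". Section 3 adds: "where applicable confirm in-network follow-up appointments are completed with an Atrium Health provider". Section 5.3 has navigators assess barriers to appointments and call at least weekly, with a C-SSRS screen at each phone contact that can lead to the patient being sent to the ED. It also says that appointments may be with "other providers in the community such as primary care or referral to a community provider".

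**The analysis.** Section 6.2 compares self-harm between arms as a yes/no outcome in a logit mixed model, by intention to treat. It also plans a per-protocol analysis of the secondary outcomes in patients who received and adhered to their assigned treatment.

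**The concern.** A diagnosis code needs an encounter at which someone can enter it. If one arm has more countable encounters, it can accumulate more codes with no difference in self-harm. Definition (d) admits outpatient encounters, and the programme acts on outpatient attendance in one arm only, as far as the documents describe. A self-harm event disclosed at an Atrium clinic visit counts; the same event in a patient seen elsewhere, or not seen, does not.

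The hypothesis is that fewer patients will be admitted when the programme is available, so more go home from the ED. Among the compared secondary outcomes, self-harm speaks most directly to how those patients fare. If outpatient coding differs by arm, an excess of codes under BH-VPN could be better detection, and a true reduction could be masked. As planned, the analysis has no way to tell these apart.

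**Working it through.** The plan gives no self-harm rate, so it has no figure to reproduce for this outcome. The check is whether its text and design inputs determine the size or sign of the detection effect.

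**Inputs from the documents**
- Admission rates: 60% under usual care and 52% under BH-VPN, from the 8-point design difference (Section 6.1).
- Navigation is offered only to patients with a discharge recommendation, and they may decline (Section 5.3).
- Analysis is by assigned day, plus a per-protocol analysis (Section 6.2).

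**Assumed, because the documents are silent**
- Uptake of navigation among discharged patients: 50% to 100%.
- Everyone not admitted is discharged and offered the programme.

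**Navigated share of the BH-VPN arm.** s = (1 − 0.52) × uptake. At 50% uptake, s = 0.48 × 0.50 = 0.24; at 100%, s = 0.48.

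**Routes to unequal coding.** Suppose there is no true difference in self-harm, and codes are rare enough for routes to add. Define:
- d_out: the net change in a navigated patient's chance of a code from an Atrium outpatient encounter. It can be negative if navigation sends patients to community providers.
- d_ED: the added chance of a code from an ED visit that follows a navigator's C-SSRS screen.
- d_adm: the added chance of a code from being admitted at the index visit. The window starts at the ED admit date, so inpatient days fall inside it; the text does not say whether index-stay codes count.

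The spurious difference in coded rate, BH-VPN minus usual care, is then

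Δ = s × (d_out + d_ED) − 0.08 × d_adm, where 0.08 = 0.60 − 0.52.

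None of the three d terms is in the documents, so Δ has no computable size.

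**Sign.** With d_ED set to zero, Δ = 0 when d_adm / d_out = s / 0.08. That is 0.24 / 0.08 = 3 at the lower share and 0.48 / 0.08 = 6 at the upper. If d_out is positive, an index admission would have to add 3 to 6 times the coding chance that navigation adds for the routes to cancel. The documents place the ratio on neither side, and if d_out is zero or negative the outpatient route does not favour extra codes under BH-VPN at all.

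**Per-protocol.** If every retained BH-VPN patient was navigated, the outpatient term is d_out instead of s × d_out. That is larger by 1/s: 1 / 0.48 = 2.1 to 1 / 0.24 = 4.2 times. The opposing term can grow too. Navigated patients are essentially those not admitted, while the usual-care arm may keep its 60% admitted, so the admission gap could approach 0.60 instead of 0.08. Both distortions are greater than under intention to treat, and the sign remains open.

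**Effect of restricting to acute encounters.** Counting only ED, inpatient and observation encounters removes s × d_out and leaves s × d_ED − 0.08 × d_adm. It isolates the outpatient route; it does not make ascertainment equal.

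**The case against.** The best case for the plan has four parts.

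1. *The pull towards Atrium is qualified.* A reader might infer that navigators steer patients into Atrium clinics. Section 3 confirms completed Atrium visits only where applicable, the synopsis asks for any appropriate provider, and Section 5.3 allows community referral, which this outcome would not capture. This stands: a net rise in Atrium outpatient encounters is plausible but not established. Nor may one infer that usual-care patients have no arranged follow-up; the documents do not describe it.
2. *Other forces oppose it.* More index admissions under usual care give that arm more inpatient coding opportunity, and intention to treat dilutes any effect of navigation. This also stands, and is why no direction is claimed.
3. *Broad capture is a legitimate pragmatic choice.* An acute-only outcome would lose clinic-recorded events and keep ED visits prompted by navigator screening. This defeats outright replacement of the outcome, but not a second version reported beside it.
4. *It is only a secondary outcome.* Correct. A reader might treat it as the trial's safety endpoint, but Section 9 designates none, and Sections 1.3 and 5.1.2 list self-harm among the secondary measures.

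It is also tempting to quantify the bias by adding assumed extra codes to a true self-harm rate in the BH-VPN arm. That is unsound: better detection of real events cannot lift the coded rate above the true rate, and every input would be invented.

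None of these answers supplies an encounter-type rule, adjudication or a sensitivity analysis for unequal ascertainment, and the plan has none.

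**Conclusion.** The point holds as an exposure to detection bias, not as a demonstrated bias. It rests on three readings of the text: (d) admits outpatient codes while (c) does not; the programme supports follow-up attendance, including Atrium visits where applicable; and no equivalent contact for usual care and no equalising step is described. Neither size nor net direction can be derived from the documents. The only figures available are conditional: a navigated share of 24% to 48% if uptake is 50% to 100%, and a per-protocol outpatient distortion 2.1 to 4.2 times that under intention to treat on the same assumption.

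If outpatient coding dominates, the result would tend to mask a benefit or suggest a false harm. If index-stay coding dominates, the tilt would favour BH-VPN. A reader might go further and say that the comparison is biased against the programme, or that an acute-only definition would cure it; the text supports neither. This is an inexpensive improvement to a secondary analysis and does not affect the primary outcome.

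**What to change.** In Sections 5.1.2(d) and 6.2:

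- Keep the any-encounter definition and add a prespecified analysis of self-harm diagnoses recorded at an Atrium ED, inpatient or observation encounter within the same window, matching the encounter types in (c).
- Fit it with the same mixed model and report it beside the any-encounter result, for both the intention-to-treat and per-protocol analyses.
- Tabulate self-harm counts by encounter type (acute or outpatient) and arm.
- State that any conclusion about self-harm depends on whether the two versions agree. An excess confined to outpatient codes should be read as possible detection.
- State that ED visits prompted by navigator C-SSRS screening and index inpatient stays remain sources of unequal detection in both versions.

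Cost: a few sentences, an encounter-type filter on data already to be extracted, and a repeat of the model. The acute-only version will have fewer events and so be less precise; because the any-encounter result is kept, nothing is lost from reporting.
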